2.2 Secondary Objectives and Endpoints

Immunogenicity	
Key secondary objectives	Key secondary endpoints

 To demonstrate non-interference of immunoglobulin G (IgG) serum responses for all Boostrix-containing antigens (diphtheria, tetanus, pertussis toxin [PT], filamentous hemagglutinin [FHA], pertactin [PRN]) at Day 29 when BPZE1 is co-administered with Boostrix (BPZE1 + Boostrix vs Boostrix). 	
 BPZE1 + Boostrix induction of serum IgG against diphtheria, tetanus, and all aP antigens (PT, FHA, PRN) compared with Boostrix at Day 29 (criteria to be assessed for diphtheria and tetanus responses per WHO guidelines).
Colonization (optional substudy only)	
Secondary objective	Secondary endpoints

 To describe colonization in each of the groups: BPZE1, BPZE1 + Boostrix, BPZE1 and BPZE1 + Boostrix, Boostrix control. 	
 Proportion of subjects with colonization at either Day 92 or 99 (B. pertussis culture or polymerase chain reaction [PCR]) with prior BPZE1 immunization following re-vaccination/attenuated challenge at Day 85 (BPZE1, BPZE1 + Boostrix, BPZE1 and BPZE1 + Boostrix, Boostrix control). Expressed as absolute proportion (Yes/No).
Mucosal secretory immunogenicity (S-IgA): WCE, PT, FHA, PRN, and any additional anti-pertussis mucosal antibodies identified during assay development using geometric mean titre (GMT) and geometric mean fold rise (GMFR) unless otherwise stated.	
NOTE: To also be tested separately in subjects who participate in the optional substudy as exploratory endpoints, to assess response following re-vaccination/attenuated challenge.	
Secondary objectives	Secondary endpoints

 To demonstrate BPZE1 induction of mucosal S-IgA immunity is non-inferior to Boostrix at Day 29 as measured by antibodies to WCE (BPZE1 vs Boostrix). 	
 BPZE1 induction of mucosal S-IgA against WCE compared with Boostrix at Day 29.

 To demonstrate BPZE1 induction of mucosal S-IgA immunity is greater than baseline at Day 29 (BPZE1, BPZE1 + Boostrix). 	
 BPZE1 induction of mucosal S-IgA at Day 29 compared to baseline.

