There is an optional open-label substudy in which enrolled subjects may elect to participate at any time from the day of enrolment through Day 85. A separate signed ICF (and separate assent when necessary) will be obtained prior to participation in the substudy. Subjects will be excluded from participating in the substudy if they meet additional exclusion criteria listed in Protocol Section 4.1.2.1. Temporary vaccination holding criteria are to be followed for the Day 85 vaccination.

Up to 120 enrolled subjects may participate in the substudy. The duration of the entire study will not change; however, additional visits/procedures starting on Day 85 will include the following:

- 3 additional visits (Days 92, 99, and 113)
- 1 additional intranasal vaccination (Day 85)
- Up to 3 additional nasal samples, including 2 of those needed for midturbinate/nasopharyngeal sample collection (Days 92 and 99) and 1 needed for leukosorb (Day 113). Subjects will contribute to all Day 85 sampling (systemic and nasal).
- Up to 2 additional blood samples (Days 85, if not already assigned to provide, and 113, including blood for cellular-mediated and systemic immunity responses)
- 1 additional subject diary (subjects to record maximum daily reactogenicity [nasal/respiratory, systemic] in a subject diary for 7 consecutive days starting the day following study vaccination)
- 1 additional test for SARS-CoV-2 within 72 hours prior to Day 85 vaccination.

All subjects participating in the open-label substudy will receive an intranasal re-vaccination/attenuated challenge with BPZE1 on Day 85. Subjects may have the planned re-vaccination/attenuated challenge deferred to a later date (up to 20 days) if pre-defined temporary exclusion criteria in Protocol Section 4.1.2.1 are met or for other personal reasons (eg, holiday, school schedule). Subjects will be monitored for at least 30 minutes after re-vaccination/attenuated challenge, with a post-vaccination evaluation for reactogenicity (nasal/respiratory, and systemic) completed prior to release from clinical observation.

Subjects will receive a subject diary on Day 85. All subjects (with assistance when needed) will record maximum daily reactogenicity in a subject diary for 7 consecutive days starting the day following re-vaccination/attenuated challenge (retrospective of the highest value in the previous 24 hours).

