For summary precision, mean and median will have one more decimal place than the reported value, SD will have two more decimal places than the reported value, minimum and maximum will have the same decimal place as the reported value. Percentages and 95% CIs will have one decimal place.

For immunogenicity analysis, it is assumed that the natural log of the data is normally distributed for the GMT/GMC/GMR, and GMFR.

GMT/GMC/GMR will be calculated as anti-logarithm of \sum (log-transformed titer/number of subjects with titer information). The 95% CI for GMT/GMC/GMR will be calculated as the anti-log transformation of upper and lower limits for a 2-sided 95% CI of the mean of the log-transformed values based on normal approximation.

For any antibody titer, if the result is reported as lower than the minimal limit of assay detection, a value equal to half of the minimal limit of assay detection will be imputed in the calculation. The minimal limit of assay detection for each of the antibody titers will be established following assay validation and prior to database lock.

GMFR will be calculated as anti-logarithm of \sum [log-transformed titer ratio of (Yi/Bi)/number of subjects with titer information], where Yi is the post-dose titer and Bi is the baseline titer for subject i. The same data summaries will be provided as GMT/GMC/GMR.

The mucosal and serum immunogenicity descriptive summaries (GMT/GMC/GMR and/or GMFR) will be provided by treatment group and by timepoint and across timepoints if applicable (all subjects), including a separate analysis after Day 85 for the open-label substudy. Analyses will include the GMT/GMC/GMR with 95% CIs and GMFRs with 95% CIs.

For seroconversion of mucosal S-IgA and serum IgA and IgG against WCE, PT, FHA, PRN, and any additional anti-pertussis antibodies identified during assay development, descriptive summaries including seroconversion rates and the 95% CIs will be provided by treatment group and by timepoint. Mucosal S-IgA will be normalized as [specific S-IgA]/[Total S-IgA (mg/mL)] and it will also be summarized using same method.

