4.3.3. Immunogenicity Analysis Set

The immunogenicity analysis set will consist of all subjects in the intent-to-treat analysis set who received study vaccine, have a baseline and at least 1 post-vaccination sample (mucosal or serum immunogenicity testing, respectively) for which valid results were reported for the test being analyzed, and have not received a licensed pertussis vaccine in the past 3 years or through Day 85 of the study nor received a tetanus/diphtheria vaccine through 29 days post study vaccination. Subjects will be classified according to the actual vaccine received.

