7.2. Study Treatments

7.2.1. Treatment Compliance and Modifications

A by-subject listing will be provided based on the ITT Analysis Set, and subjects in the optional substudy will also be included.

8. Immunogenicity Analysis

Immunogenicity Analyses will be performed based on Per Protocol Immunogenicity Analysis Set, and sensitivity analyses will be performed where specified.

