8.3.1. Analyses of Secondary Mucosal Secretory Immunogenicity (S-IgA) Endpoints

Descriptive statistics (GMC/GMR [also known as GMT per protocol], GMFR, seroconversion) for mucosal S-IgA against WCE, PT, FHA, PRN, and any other anti-pertussis mucosal antibodies identified during assay development will be presented at each timepoint and by treatment groups. Mucosal S-IgA will also be normalized as [specific S-IgA]/[Total S-IgA (mg/mL)].

A non-inferiority hypothesis will be tested to demonstrate BPZE1 can adequately induce pertussis specific mucosal S-IgA responses at Day 29 against WCE (GMC/GMR and GMFR) compared with Boostrix. A two-sample t-test will be used to compare the natural log-transformed GMC/GMRs between BPZE1 and Boostrix groups. The non-inferiority margin is set at 2-fold decrease or -0.693 on natural log scale. Non-inferiority will be demonstrated if the lower limit of the 95% CI of group difference on natural log scale is greater than -0.693.

To test the hypothesis that BPZE1 can adequately induce pertussis-specific mucosal S-IgA responses at Day 29, Day 85, and Day 169/EOS against WCE, PRN, PT, and FHA compared with baseline by treatment group, separate paired t-tests will be used to compare the natural log-transformed GMC/GMR at Day 29, Day 85, Day 169/EOS with the natural log-transformed GMC/GMR at baseline within each of treatment groups. The corresponding 95% CIs will be calculated on the natural log scale, then both lower and upper limits will be exponentiated to obtain the 95% CIs on the original scale.

A non-inferiority hypothesis will be tested to demonstrate that BPZE1+Boostrix induction of mucosal S-IgA immunity is non-inferior to BPZE1 at Day 29 and Day 169/EOS. Separate ANCOVA models that include baseline S-IgA and treatment group as covariates will be used to compare the natural log-transformed GMCs/GMRs between BPZE1+Boostrix and BPZE1 groups. The non-inferiority objective will be demonstrated if the lower limit of the 95% CI of group difference on the natural log scale is greater than -0.693.

Subgroup analysis by age group (6-10 years and 11-17 years, inclusive, and 10 – 17 years [for requested analyses]), time since last aP vaccination prior to study entry (<median time, \geq median time), or other baseline demographics, and by baseline antibody level (by quantile) will be conducted to examine differential responses to induction of mucosal S-IgA at Day 29 for BPZE1

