Note: Grade 0 will be the classification if the observation is less than a Grade 1. Any grade 3 reactogenicity event that leads to an unscheduled visit to a healthcare provider will be recorded as an MAAE.

^a Temperature may be oral, tympanic, or noncontact (clinic only). Temperature greater than 40.0 °C (104.0 °F) is considered an SAE and subjects should seek medical attention immediately.

Source: Adapted from DAIDS Version 2.1, 2017.

9.2.Unsolicited Adverse Events

Unsolicited AEs will be coded according to Medical Dictionary for Regulatory Activities (MedDRA) latest version. Unless otherwise specified, unsolicited AEs will be summarized by System Organ Class (SOC), FDA Medical Query (FMQ) and Preferred Term (PT), with SOCs sorted in the alphabetical order and PTs within each SOC in descending order of subject incidence.

TEAE is defined as an AE that starts or an existing AE that worsens on or after the date of vaccination. AEs will be summarized by treatment groups, age group, and main study and substudy separately. In general AEs will be summarized from Day 1 to end of study for overall and subjects in substudy. AEs from Day 85 to end of study for subjects in substudy will be summarized separately. Between screening and Day 1, AEs will be collected if classified as SAEs or if considered related to study procedure or study involvement. All AEs regardless of causality will be recorded for 28 days after any vaccination/challenge and summarized. All AESI and SAE will be recorded and summarized from the time of vaccination to Day 169/EOS. All MAAEs occurring through 84 days following any vaccination (and through EOS) will be recorded and summarized.

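### The SAP's Day 169/EOS secondary immunogenicity tests do not remove data collected after the open-label Day 85 BPZE1 dose, so they do not estimate single-dose durability or the single-dose contrast between groups

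*SAP*

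**What the plan says.** SAP 3.1 sets the substudy: "Up to 120 enrolled subjects may participate in the substudy", and "All subjects participating in the open-label substudy will receive an intranasal re-vaccination/attenuated challenge with BPZE1 on Day 85". Participation is open to all three randomised groups. For a Boostrix control the Day 85 dose is a first exposure to BPZE1; for the other two groups it is a second.

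SAP 4 describes the descriptive immunogenicity summaries as given "by treatment group and by timepoint and across timepoints if applicable (all subjects), including a separate analysis after Day 85 for the open-label substudy". The note to the secondary endpoints in Protocol 2.2, repeated in SAP 3.2.2.3, says of these endpoints: "To also be tested separately in subjects who participate in the optional substudy as exploratory endpoints".

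The opening of SAP 8 fixes the population for the tests: "Immunogenicity Analyses will be performed based on Per Protocol Immunogenicity Analysis Set, and sensitivity analyses will be performed where specified". The Day 169/EOS tests are:

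- S-IgA against baseline within each group (8.3.1), and serum IgA and IgG against baseline in the two BPZE1 groups (8.3.2), by paired t-test.
- Whether "BPZE1+Boostrix induction of mucosal S-IgA immunity is non-inferior to BPZE1 at Day 29 and Day 169/EOS" (8.3.1, ANCOVA with baseline).
- BPZE1 and BPZE1 + Boostrix against Boostrix, for S-IgA (8.3.1) and for serum IgA and IgG as non-inferiority (8.3.2), by ANCOVA.

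The parent set (SAP 4.3.3) requires that subjects "have not received a licensed pertussis vaccine in the past 3 years or through Day 85 of the study". The Per-Protocol set (4.3.4) adds further exclusions. One of them concerns missing substudy cultures; none concerns samples taken after the Day 85 BPZE1 dose. The window table in SAP 4.5 assigns late samples from substudy subjects to the same EOS/Day 169 visit. The only estimand table (8.1) is for Day 29 and lists no intercurrent events.

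**The concern.** The trial's title and rationale concern one dose of BPZE1. The Day 169 objectives ask whether the response to that dose lasts and how the groups compare at six months. If a subject has a further BPZE1 dose on Day 85, the Day 169 sample reflects both doses. In the Boostrix arm it reflects a first BPZE1 dose that the single-dose comparison supposes was never given.

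Two errors become possible. A response that had waned could still test as above baseline because some subjects were boosted. In comparisons with Boostrix, re-vaccinating part of both arms pulls them together, which can make non-inferiority too easy to claim or can shrink a real advantage. The plan also has an exploratory objective asking whether re-vaccination alters Day 169 titres, so pooling the two populations in the secondary tests assumes away a question that the plan itself leaves open.

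Two smaller rules raise the same issue. First, the licensed-vaccine criterion in 4.3.3 (evidently meant for vaccine given outside the study) removes a subject entirely. A vaccine on Days 30 to 85 therefore discards valid Day 29 data, while one after Day 85 triggers no exclusion under that criterion. Second, SAP 9.2 states: "In general AEs will be summarized from Day 1 to end of study for overall and subjects in substudy". That overall summary places events after the Day 85 dose under the randomised arm.

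**Working it through.** **The plan's own figures.** The SAP gives no power for Day 169. Its Day 29 figures reproduce. A paired t-test with n = 108, effect size 0.35 and two-sided 0.05 has power 95.0% (stated 95%), and squared this is 90.2% (stated 90%). Non-inferiority power from SAP Table 4-2 with 108 per group is 97.0% for PT, 100% for FHA and 88.3% for PRN (stated 97.0%, 100%, 88.2%).

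**Share affected.** The documents give a cap of 120 and no split by arm. If the cap is reached and uptake is even, the share is f = 120/360 = 1/3, that is 40 per arm.

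**Durability against baseline.** Assume that single-dose titres are back at baseline (GMFR 1) and that re-vaccinated subjects have an r-fold rise. The pooled log mean is f·ln(r), and the pooled SD is √(σ² + f(1−f)·ln(r)²). With f = 1/3, σ = 1 (assumed) and n = 108:

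| r | log mean | pooled GMFR | pooled SD | noncentrality | chance of success |
|---|---|---|---|---|---|
| 1.5 | 0.135 | 1.14 | 1.018 | 1.38 | 28% |
| 2 | 0.231 | 1.26 | 1.052 | 2.28 | 62% |
| 3 | 0.366 | 1.44 | 1.126 | 3.38 | 92% |

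The nominal rate in this direction is 2.5%. Using the smallest and largest planning SDs in Table 4-2 (0.8158 and 1.4363) as stand-ins for σ, the ranges are 16–38%, 37–77% and 70–97%. With σ = 1, r = 2 and lower uptake, the chance is 10% at f = 0.1 and 28% at f = 0.2.

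**Non-inferiority to Boostrix.** Assume that the true single-dose ratio is exactly 0.5, the margin, and that the Day 85 dose equalises re-vaccinated subjects across arms. The pooled log difference is (1−f)·ln(0.5). At f = 1/3 this is −0.462, a ratio of 0.63. The noncentrality is (0.693 − 0.462)/(SD·√(2/108)), which is 2.08 at SD 0.8158 and 1.18 at SD 1.4363. False non-inferiority is then about 54% and 22%, instead of 2.5%. At f = 0.1 it is 5–9%, and at f = 0.2 it is 10–24%.

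**The opposite direction.** Under the same equalising assumption, a true two-fold advantage over Boostrix would appear as 2^(2/3) = 1.59.

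**What remains after exclusion.** Take 40 re-vaccinated per arm. If dropout applies to the remaining 80, 0.9 × 80 = 72 are evaluable. If all 40 come out of the 108 evaluable, 68 remain. With Day 29 planning inputs carried over to Day 169:

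| n per arm | paired effect 0.35 | PT-type NI | FHA-type NI | PRN-type NI | 95% CI half-width at SD 1 |
|---|---|---|---|---|---|
| 108 | 95% | 97% | 100% | 88% | 0.27 |
| 72 | 83% | 88% | 99.8% | 73% | 0.33 |
| 68 | 81% | 86% | 99.8% | 70% | 0.34 |

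**The case against.** The strongest reply is that the plan never states that re-vaccinated subjects stay in the Day 169 tests. The all-subjects sentence in SAP 4 concerns descriptive summaries, and a separate analysis after Day 85 could be read as moving participants out. That point about the sentence stands: for the tests, inclusion follows from the set definitions and from the lack of any exclusion. The rest of the text favours inclusion, however. Substudy testing is described as additional, and where the SAP wants a restricted population, as in 8.4.1, it says so.

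A reader might infer that the randomised comparison itself is lost. The documents do not support that. Analysing everyone as randomised remains a valid comparison of policies that include an optional later BPZE1 dose. What is lost is the single-dose reading, and the SAP does not say which of the two it intends.

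SAP 8.4.2 and 8.4.3 already summarise Day 169 results by participation within each arm, so unboosted results will be visible. This stands, but those results do not feed the formal tests.

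A reader might also infer that adverse events after re-vaccination are generally mixed into the Day 1 results. They are not. SAP 9.2 itself summarises substudy events from Day 85 separately, and the Section 9 preamble, 9.2.2 and 9.2.3 separate the two vaccinations. Only the overall Day 1-to-EOS summary is affected. Similarly, an outside pertussis vaccine after Day 85 could be caught by the protocol-deviation exclusion in 4.3.4, though only through clinical review.

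Finally, the effect sizes are assumed. In Protocol 1.1, adults kept their antibodies for nine months, and BPZE1-induced mucosal immunity was associated with protection from colonisation by a later BPZE1 dose. A small boost in primed arms is therefore plausible.

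**Conclusion.** The concern holds for the secondary Day 169/EOS tests in SAP 8.3.1 and 8.3.2. As written they combine subjects with and without the Day 85 dose, with no exclusion, no participation term and no stated estimand, so they cannot be read as single-dose durability or as single-dose contrasts.

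The size cannot be fixed from the documents. It rests on the substudy filling evenly to its cap, on an assumed effect of the second dose, and on an assumed SD; at low uptake or with a weak boost it is modest.

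It does not reach the Day 29 primary and key secondary analyses, the study's success criterion, or the Day 85 samples taken before the dose. It should be fixed, but it does not threaten the trial's main conclusions.

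**What to change.** - **Estimand.** In SAP 4.3.3, 4.3.4, 8.3.1 and 8.3.2, name the Day 85 BPZE1 dose as an intercurrent event for Day 169. Exclude immunogenicity data collected after it from the main Day 169 tests, and keep all earlier data from the same subjects.
- **Opt-in selection.** Protocol 5.1 accepts that opting in may bring bias, and excluding participants carries that bias into these tests. Compare baseline and Day 85 titres by participation, and adjust the between-group Day 169 models for them. Day 85 titre is itself a response to vaccination, so as a plain covariate it would absorb part of the vaccine effect. A repeated-measures model of Days 29, 85 and 169 with baseline as covariate, or weighting for participation, avoids this. The repeated-measures model also copes with lead-in subjects outside the substudy, who need not give Day 85 samples.
- **Supplementary results.** Report the all-subjects analysis as supplementary, labelled treatment-policy, and re-vaccinated subjects in 8.4.
- **Non-study pertussis vaccine.** Censor by visit from the date of vaccination, so that valid Day 29 data stay in and later Day 169 data come out.
- **Adverse events.** In 9.2, cut the overall Day 1-to-EOS summary at re-vaccination, or label it as covering both periods.

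The cost is SAP text and programming, plus precision. If the substudy fills evenly, about 68 to 72 evaluable subjects per arm remain at Day 169, with the loss of power and interval width shown in the last table of the working. The change should be made before unblinding, because a choice of Day 169 population made later would be open to challenge.

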4.1. Sample Size

Approximately 360 subjects will be enrolled and randomly assigned (1:1:1) to 1 of 3 treatment groups (refer to Table 3-1) to contribute to safety and efficacy assessments. Enrollment will be

operationally managed at the study level to maintain a minimum number of subjects enrolled in 2 age groups: 6 to 10 years, inclusive; and 11 to 17 years, inclusive. It is estimated that a 10% drop out rate will occur, allowing for approximately 108 evaluable subjects per treatment group.

4.1.1. Sample Size for Primary Immunogenicity Endpoints

The sample size is based on calculations to achieve adequate response on Day 29 over baseline of mucosal S-IgA for WCE assay in the BPZE1 and BPZE1 + Boostrix groups. Assuming the GMT follows a log-normal distribution, by applying a natural logarithmic transformation of the GMT, a paired t-test will be used to test the difference of mucosal S-IgA against WCE at Day 29 compared with baseline (equivalent to natural logarithmic transformation of the GMFR). With an effective sample size of N=108 subjects per group, the study provides 95% power for detecting an effect size of 0.35 for each of the two primary comparisons with a two-sided significance level of 0.05. By multiplying the power for each of the two comparisons, the study provides an overall power of 90% (=95%*95%) for testing both primary comparisons (BPZE1, BPZE1+Boostrix). Factoring in an estimated 10% drop-out rate, each treatment group would include approximately 120 subjects for a total of approximately 240 subjects in the study for the primary analysis. An additional 120 subjects are randomized to the Boostrix group for the assessment of non-interference resulting in a total of approximately 360 subjects in the study.

4.1.2. Sample Size for Key Secondary Endpoints

To demonstrate non-interference of IgG serum responses for the Boostrix-containing antigens (diphtheria, tetanus) at Day 29 when BPZE1 is co-administered with Boostrix (BPZE1 + Boostrix vs Boostrix), the test for non-inferiority of BPZE1 + Boostrix to Boostrix for the proportion with titer ≥ 0.1 IU/mL (for diphtheria, tetanus) has power exceeding 92% with approximately N=120 subjects per treatment group, assuming a noninferiority margin of 0.1, one-sided significance level of 0.025, 10% drop-out rate and the proportion with titer ≥ 0.1 IU/mL for the Boostrix treatment being at least 0.95.

Table 4-1 Power for Non-Inferiority of BPZE1/Boostrix to Boostrix for the proportion of titer ≥ 0.1 IU/mL

Parameter			Power ^{**}			
p_B [*]	$p_{BBP,0}$ ⁺	$p_{BBP,1}$ [#]	N=120***	N=135***	N=150***	N=165***
0.92	0.82	0.92	77.3%	81.8%	85.7%	88.7%
0.95	0.85	0.95	92.1%	94.6%	96.5%	97.7%
0.97	0.87	0.97	99.1%	99.0%	99.8%	99.9%

^{*}: p_B is the proportion of titer ≥ 0.1 IU/mL for the Boostrix treatment

⁺: $p_{BBP,0}$ is the proportion of titer ≥ 0.1 IU/mL for the BPZE1/Boostrix treatment under the null hypothesis H_0

[#]: $p_{BBP,1}$ is the proportion of titer ≥ 0.1 IU/mL for the BPZE1/Boostrix treatment under the alternative hypothesis H_1

^{**}: with one-sided significance levels of 0.025 and non-inferiority margin of 0.1

***: Effective sample size accounts for 10% dropout. For sample size of 120, 135, 150, 165 per group, the effective sample size is 108, 121, 135, 148, respectively, after accounting for 10% dropout.

To demonstrate non-interference of IgG serum responses for the Boostrix-containing antigens (PT, FHA, PRN) at Day 29 when BPZE1 is co-administered with Boostrix (BPZE1 + Boostrix vs Boostrix), the tests for non-inferiority of BPZE1 + Boostrix to Boostrix for each of the three IgG parameters (PT/FHA/PRN) have power of 97%, 100%, and 88%, respectively, for detecting between group differences as observed in study IB-200P, with approximately 120 subjects per treatment group, one-sided significance levels of 0.025, 10% drop-out rate and non-inferiority margin of -0.693 on the natural log scale (or 2-fold decrease on the original scale).

Table 4-2: Power for Non-Inferiority of BPZE1/Boostrix to Boostrix for serum IgG parameters

Serum IgG Parameter	Mean Diff Used for Sample Size Calculation (based on previous adult Ph2b study) (on natural log)	StdDev ⁺ (on natural log)	Power**			
			N =120 per group*	N =135 per group*	N =150 per group*	N =165 per group*
PT	-0.234	0.8759	97.0%	98.2%	99.0%	99.4%
FHA	-0.019	0.8158	100%	100%	100%	100%
PRN	-0.075	1.4363	88.2%	91.5%	94.1%	95.8%

*: Effective sample size accounts for 10% dropout. For sample size of 120, 135, 150, 165 per group, the effective sample size is 108, 121, 135, 148, respectively, after accounting for 10% dropout.

**: with one-sided significance levels of 0.025 and non-inferiority margin of -0.693 (=natural log(0.5))

